7.5.8 WHO Ordinal Scale for Clinical Improvement

Number and proportion of participants who achieve a score of 1 on the WHO Ordinal Scale for Clinical Improvement on Days 8 and 15 will be tabulated by treatment group and Baseline WHO Ordinal Scale and compared in a way similar to the analysis of ICU Admissions in Section 7.5.5.

The corresponding 95% binomial confidence interval will also be reported. Sample size permitting, Wilson's method will be used to derive these confidence intervals. The difference in proportions will also be reported with the corresponding 95% confidence interval using Newcombe's method. Should the number of observed admissions be small, the exact distribution will be used instead of the normal approximation to derive the confidence intervals.

Similarly, the number and proportion of participants who achieve 2-point improvement from baseline in the WHO Ordinal Scale for Clinical Improvement on Days 8 and 15 will be analyzed based on Full Analysis Set. Median number of days to a 2-point improvement will be tabulated by treatment group and compared in a way similar to the analysis of duration of COVID-19 symptoms in Section 7.5.3. The same analysis will be provided in the Safety Analysis Set.

7.5.9 Thromboembolic Events

All adverse events will be reviewed in a blinded fashion prior to the database lock by team members with appropriate background and training. The team will identify adverse events with an onset date within 15 days after enrollment that may be considered thromboembolic.

Incidence and severity of thromboembolic events will be tabulated by treatment group and compared in a way similar to the analysis of ICU Admissions in Section 7.5.5.

7.5.10 Inflammation Markers Associated with Acute Respiratory Distress Syndrome (ARDS)

The following inflammation markers associated with acute respiratory distress syndrome will be analyzed at a central lab: CRP, IL-6, TF, MCP-1, and IP-10. An inflammation marker is considered abnormal if the reported value is > ULN.

Incidence of abnormal inflammation markers at Day 8 will be tabulated by treatment group and compared in a way similar to the analysis of ICU Admissions in Section 7.5.5.

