To evaluate the effect on subjective symptoms of COVID-19	• Median time (in days) to resolution of subjective symptoms assessed by the Investigator to be potentially due to COVID-19 including: fever, cough (productive or non-productive), sore throat, malaise, headache, muscle pain, gastrointestinal symptoms (i.e., nausea, vomiting, or diarrhea), shortness of breath (with or without exertion), and respiratory distress
To evaluate progression of COVID-19 from moderate or	Proportion of participants who's COVID-19 progresses to Severe or Critical (Appendix 4) within 15 days after enrollment
severe to more severe (i.e., moderate to severe, moderate to critical, or severe to critical)	Proportion of participants requiring ICU admission within 15 days after enrollment
, , , , , , , , , , , , , , , , , , ,	Mean change from baseline (BL) in SOFA score on Day 8 and Day 15
To evaluate the effect of ANA001 on requirement for oxygen and/or assisted	• Proportion of participants requiring supplemental O 2 , high-flow nasal cannula (HFNC) oxygen, noninvasive positive pressure ventilation (NIPPV) or mechanical ventilation on Day 8 and Day 15
ventilation	Mean number of days on mechanical ventilation within 15 days after enrollment
	Mean number of oxygenation-free days within 15 days after enrollment
To evaluate time to resolution of the WHO Ordinal Scale for	Proportion of participants with an improvement in the WHO Ordinal Scale for Clinical Improvement (Appendix 1) on Day 8 and Day 15
Clinical Improvement	Median time (in hours) to 2-point improvement in the WHO Ordinal Scale for Clinical Improvement
To evaluate the effect of ANA001 on thromboembolic events	Incidence and severity of thromboembolic events within 15 days after enrollment
To evaluate the relationship of ANA001 and markers of inflammation associated with acute respiratory distress syndrome (ARDS)	• Incidence of abnormal markers of inflammation (CRP, IL-6, TF, MCP-1, and IP-10) on Day 8
To evaluate the relationship between ANA001 and viral dynamics	
 
Mean change in viral load from baseline (BL) on Days 1, 4, 8, 15, and 28
 
Mean time (in days) to viral load undetectable by nasopharyngeal (NP) swab
 

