# 6.3.1 Day 1 Assessments

Procedures to be performed and information to be collected on Day 1:

- Height and weight for body mass index (BMI). If a participant is unable to be measured for height and weight, stated height and weight is acceptable.
- NEWS2 (Appendix 2), vital signs, severity of the participant's COVID-19 (Appendix 4), and assessment for presence of subjective clinical signs and symptoms of COVID-19 will be assessed and include presence or absence of: fever, cough (productive or non-productive), sore throat, malaise, headache, muscle pain, gastrointestinal symptoms (i.e., nausea, vomiting, or diarrhea), shortness of breath (with or without exertion), and respiratory distress. Day 1 assessments should be done before the first dose of study drug.
- Record SpO2 on room air and need for supplemental nasal cannula oxygen (including flow rate) if applicable. For patients on supplemental oxygen, SpO2 should be recorded with at least 30 continuous minutes of oxygen.
- A complete physical examination, excluding a genitourinary (GU) examination.
- Administration of study drug (ANA001 or matching placebo). Study drug should be taken with a meal (or NG/OG/PEG tube feeding if applicable).
- Serum chemistry (to be collected before initial dosing), including blood urea nitrogen (BUN), creatinine, sodium, potassium, chloride, carbon dioxide, glucose, direct bilirubin, total bilirubin, alkaline phosphatase (ALP), aspartate aminotransferase (AST), alanine aminotransferase (ALT).
- Hematology and coagulation tests (to be collected before initial dosing) including a complete blood count (CBC), which consists of hemoglobin, hematocrit, total WBC count with a 5-part differential, platelet count, plus a partial thromboplastin time (aPTT), prothrombin time (PT), and an international normalized ratio (INR).
- D-dimer, CRP, cardiac troponin, LDH, and ferritin samples collected for central laboratory testing (to be collected before initial dosing).
- NP swab for confirmation of SARS-CoV-2 with RT-PCR (local site laboratory) per site SOC (to be collected before initial dosing) if part of standard-of-care.
- NP swab for confirmation of SARS-CoV-2 with RT-PCR (central laboratory) (to be collected before initial dosing).

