- PK sample collection: Study Part 1 Only: See Appendix 6 for PK sample collection schedule. Refer to the Central Laboratory Manual for additional sample collection and processing instructions. PK samples should be collected in relation to the morning dose of study drug administration.
- WHO Ordinal Scale for Clinical Improvement score (Appendix 1) assessment should be collected/recorded daily and any time the WHO Ordinal Scale for Clinical Improvement score changes. The WHO Ordinal Scale for Clinical Improvement should be recorded with the corresponding date and time of assessment (if unchanged) or with the date and time reflecting the numerical change in the score (if changed).

- Chest X-ray per local standard-of-care.
- AE assessment.
- All systemic concomitant medications (Section 7.4).
- Sequential Organ Failure Assessment (SOFA) score (to be performed at baseline for all participants; Appendix 3).
- Blood for exploratory tests (e.g., IL-6, tissue factor, MCP-1 and IP-10). Blood sample is to be collected before initial dosing.

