- Daily administration of study drug (ANA001 or matching placebo). Study drug should be taken with a meal (or NG/OG/PEG tube feeding if applicable). Total duration of study drug administration is a 7-day course of treatment (i.e., 14 scheduled doses comprised of 56 capsules in total). Participants may be discharged before completing 14 doses and are to be given dosing instructions, the remainder of their therapy, and a diary to record all study drug doses taken.
- Daily serum chemistry (pre-dose), including blood urea nitrogen (BUN), creatinine, sodium, potassium, chloride, carbon dioxide, glucose, direct bilirubin, total bilirubin, alkaline phosphatase (ALP), aspartate aminotransferase (AST), alanine aminotransferase (ALT).

- Daily hematology and coagulation tests (pre-dose) including a complete blood count (CBC), which consists of hematocrit, hemoglobin, total WBC count with a 5-part differential, platelet count, plus a partial thromboplastin time (aPTT), prothrombin time (PT), and an international normalized ratio (INR).
- D-dimer, CRP, and ferritin (to be collected pre-dose on Day 4 and Day 8 only) for central laboratory testing. Cardiac troponin and LDH (to be collected Day 8 or EOT) for central laboratory testing.
- NP swab for confirmation of SARS-CoV-2 with RT-PCR (local site laboratory) per site SOC if part of standard-of-care.
- NP swab for SARS-CoV-2 testing with RT-PCR (to be collected on Day 4 and 8) for central laboratory testing.
- PK sample collection: Study Part 1 Only: See Appendix 6 for PK sample collection schedule. Refer to the Central Laboratory Manual for additional sample collection and processing instructions (Day 1, 2, 3 or Day 4). PK samples should be collected in relation to the morning dose of study drug.
- Daily WHO Ordinal Scale for Clinical Improvement score (Appendix 1) assessment should be collected/recorded daily and any time the WHO Ordinal Scale for Clinical Improvement score changes. The WHO Ordinal Scale for Clinical Improvement should be recorded with the corresponding date and time of assessment (if unchanged) or with the date and time reflecting the numerical change in the score (if changed).
- Chest X-ray per local standard-of-care.
- Daily AE assessment.
- All systemic concomitant medications (Section 7.4).
- SOFA score (to be performed daily only for participants who are admitted in the ICU; Appendix 3).
- Blood for exploratory tests (e.g., IL-6, tissue factor, MCP-1 and IP-10) on Day 8.

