4.2.2 Exploratory Efficacy Endpoints

The following are the exploratory efficacy endpoints of Part 1 of this study:

- Mean change from baseline in the NEWS-2 total score on Day 15
- Mean number of days on rescue treatment (COVID-19 therapies that are FDA approved or have emergency-use authorization) within 15 days after enrollment.
- Median time (in days) to resolution of subjective symptoms assessed by the Investigator to be potentially due to COVID-19 including: fever, cough (productive or non-productive), sore throat, malaise, headache, muscle pain, gastrointestinal symptoms (i.e., nausea, vomiting, or diarrhea), shortness of breath (with or without exertion), and respiratory distress
- Proportion of participants who's COVID-19 progresses to Severe or Critical within 15 days after enrollment
- Proportion of participants requiring ICU admission within 15 days after enrollment
- Mean change from baseline in SOFA score on Days 8 and 15
- Proportion of participants on Days 8 and 15 requiring:
 - Supplemental oxygen
 - High flow nasal cannula (HFNC) oxygen
 - Non-invasive positive pressure ventilation (NIPPV)
 - Mechanical ventilation
- Mean number of days on mechanical ventilation within 15 days after enrollment
- Mean number of oxygenation-free days within 15 days after enrollment

- Proportion of participants who achieve a score of 1 on the WHO Ordinal Scale for Clinical Improvement on Days 8 and 15
- Median time (in hours) to a 2-point improvement in the WHO Ordinal Scale for Clinical Improvement
- Incidence and severity of thromboembolic events within 15 days after enrollment
- Incidence of abnormal markers of inflammation to include CRP, IL-6, TF, MCP-1, and IP-10 on Day 8
- Mean change in viral load from baseline on Days 1, 4, 8, 15, and 28
- Median number of days to viral load undetectable by nasopharyngeal (NP) swab

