7.5.5 ICU Admission

The number and proportion of participants requiring ICU admission at any time within the first 15 days after enrollment will be tabulated by treatment group and Baseline WHO Ordinal Scale for Clinical Improvement score. The corresponding 95% binomial confidence interval will also be reported. Sample size permitting, Wilson's method will be used to derive these confidence intervals. The difference in proportions will also be reported with the corresponding 95% confidence interval using Newcombe's method. Should the number of observed admissions be small, the exact distribution will be used instead of the normal approximation to derive the confidence intervals.

Participants who did not get admitted to ICU will not contribute to this analysis

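### SAP 7.5.10 compares five inflammation markers only as the share above ULN on Day 8, leaving the pre-dose value out of the comparison; a baseline-adjusted log-scale analysis should be added beside it

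*SAP*

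**What the plan says.** The endpoint comes from the protocol. Tables 2 and 3 (Protocol Section 3) define it for Part 1 and Part 2; the Part 2 wording is "Incidence of abnormal markers of inflammation (CRP, IL-6, TF, MCP-1, and IP-10) on Day 8". SAP Section 4.2.2 repeats it for Part 1: "Incidence of abnormal markers of inflammation to include CRP, IL-6, TF, MCP-1, and IP-10 on Day 8".

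SAP Section 7.5.10 makes it operational with a cut-off, "An inflammation marker is considered abnormal if the reported value is > ULN", and a comparison, "Incidence of abnormal inflammation markers at Day 8 will be tabulated by treatment group and compared in a way similar to the analysis of ICU" (the reference is to Section 7.5.5). The method carried over is a proportion per arm with a Wilson or exact interval, and "The difference in proportions will also be reported with the corresponding 95% confidence interval using Newcombe's method". Neither section brings in a baseline marker value.

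That value exists for all five markers. Protocol Section 6.3.1 requires on Day 1 "Blood for exploratory tests (e.g., IL-6, tissue factor, MCP-1 and IP-10). Blood sample is to be collected before initial dosing", and for CRP "D-dimer, CRP, cardiac troponin, LDH, and ferritin samples collected for central laboratory testing (to be collected before initial dosing"). Section 6.3.2 requires "Blood for exploratory tests (e.g., IL-6, tissue factor, MCP-1 and IP-10) on Day 8", and CRP before dosing on Day 4 and Day 8.

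**The concern.** The protocol synopsis states the hypothesis that ANA001 reduces viral load and inflammation. These markers are the direct readout of the second half. Viral load is analysed as log-transformed change from baseline (SAP 7.5.11), whereas the markers get a cut-off on a single day.

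Two consequences follow from the wording alone:

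- CRP falling from 20 to 2 times ULN and CRP rising from 2 to 20 times ULN are both scored abnormal.
- A participant at or below ULN on both days and one who moved from above to below ULN are both scored normal.

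The comparison registers only which side of ULN a value lies on at Day 8. With 30 per arm in Part 1, that leaves an imprecise pharmacodynamic estimate when a more precise one could be had from samples already drawn.

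**Working it through.** The documents state no power, effect size, SD or abnormal rate for these markers, so there is no figure of the plan's own to reproduce.

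**Inputs from the documents.** 30 per arm in Part 1 (Protocol 9.1.1); two-sided 0.05 (SAP 7); the binary rule and method (SAP 7.5.10 and 7.5.5).

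**Assumptions, none from the documents.** Markers are log-normal and treatment shifts the log mean. The placebo share above ULN on Day 8, p, is 0.50 to 0.95. The Day 1 to Day 8 correlation on the log scale, rho, is 0 to 0.7.

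**Step 1: cost of the cut-off.** For a small shift, the binary result keeps a fraction E = phi(c)^2 / [p(1 - p)] of the information in the continuous Day 8 value, where c is the normal cut-point leaving p above it.

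- p = 0.5: 0.3989^2 / 0.25 = 0.637
- p = 0.8: 0.2800^2 / 0.16 = 0.490
- p = 0.9: 0.1755^2 / 0.09 = 0.342
- p = 0.95: 0.1031^2 / 0.0475 = 0.224

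**Step 2: cost of omitting Day 1.** Adjusting for the log Day 1 value multiplies the residual variance by 1 - rho^2: 1, 0.91, 0.75 and 0.51 for rho = 0, 0.3, 0.5 and 0.7.

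**Step 3: combined loss** = 1 - E(1 - rho^2).

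| p above ULN | rho = 0 | 0.3 | 0.5 | 0.7 |
|---|---|---|---|---|
| 0.50 | 36% | 42% | 52% | 68% |
| 0.70 | 42% | 48% | 57% | 71% |
| 0.80 | 51% | 55% | 63% | 75% |
| 0.90 | 66% | 69% | 74% | 83% |
| 0.95 | 78% | 80% | 83% | 89% |

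At rho = 0.5, 30 per arm analysed as planned is worth about 30 x 0.637 x 0.75 = 14 per arm of the adjusted analysis when p = 0.5, and 30 x 0.342 x 0.75 = 8 per arm when p = 0.9.

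**Step 4: power as a cross-check.** With a treatment effect of d SD on the log scale, the active-arm share above ULN is 1 - Phi(c + d). For p = 0.9 and d = 0.75 it is 1 - Phi(-1.282 + 0.75) = 0.702. The two-proportion normal approximation then gives power 0.48. For the adjusted analysis at rho = 0.5, the standardised difference is 0.75 / [sqrt(0.75) x sqrt(2/30)] = 3.35, and power is Phi(3.35 - 1.96) = 0.92.

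| Assumed effect, 30 per arm | Binary, p = 0.5 to 0.95 | Adjusted log analysis, rho = 0 to 0.7 |
|---|---|---|
| 0.5 SD | 0.18 to 0.32 | 0.49 to 0.77 |
| 0.75 SD | 0.37 to 0.62 | 0.83 to 0.98 |

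A simulation of 4,000 trials at d = 0.75, p = 0.9 and rho = 0.5 gave 0.49 for a Newcombe interval excluding zero and 0.91 for analysis of covariance.

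**Step 5: is the Day 1 value used elsewhere?** SAP 7.6.2 summarises laboratory values and change from baseline by visit, and Appendix C lists CRP with percentage-change limits. That is descriptive and in the Safety set (SAP 7.6). It is also built to flag abnormality: an 80% or greater fall in CRP falls at or beyond the limit Appendix C sets for decreases. IL-6, TF, MCP-1 and IP-10 are not in Appendix C and have no other named analysis.

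**The case against.** Several stronger readings are tempting, and the documents do not support them.

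- **That most of the information is lost.** A reader might infer this, but it depends on inputs the documents do not give. With p of 0.5 to 0.7 and rho of 0.3 or less, the loss is 36-48%. It passes half when rho is at least 0.5 or when about 80% or more of placebo participants are still above ULN.
- **That the SAP ignores Day 1 for all five markers.** For CRP, change from baseline is shown descriptively through 7.6.2 and Appendix C. Only the other four have no other named analysis.
- **That the SAP introduced the dichotomy.** The protocol defines an incidence endpoint for both parts, and the SAP implements it. There is no departure to correct, so replacing the endpoint would itself create one.
- **That a real effect would be declared absent.** SAP 7.5.5 specifies a difference with a 95% interval and names no test, and Protocol 9.3 plans no formal inference in Part 1. Chance baseline imbalance under randomisation costs precision; it is not bias.

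It can also be said that the markers serve one of nine exploratory objectives (SAP 2.3) in a part designed for safety. That stands, and it limits the weight of the point. It does not explain why values already collected should go unused when an added estimate is inexpensive.

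**Conclusion.** The point holds as an efficiency improvement, not as an error. The Day 8 comparison in SAP 7.5.10 cannot separate a large fall from a rise when both stay above ULN, nor normalisation from normality throughout. That much needs no assumptions.

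The size does: about 36-89% of the information in a baseline-adjusted continuous analysis, for log-normal markers, 50-95% above ULN on Day 8 and a correlation of 0-0.7. The loss is substantial over that whole range, but its exact level is unknown for any marker. The calculation also assumes 30 complete pairs per arm, which missing samples would reduce.

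The effect on the trial is modest. The endpoint is exploratory, and no primary or secondary endpoint depends on it.

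**What to change.** Keep the Day 8 incidence above ULN in SAP 7.5.10 as the protocol-defined endpoint and add, in the Full Analysis Set:

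1. For each marker, an analysis of covariance of the log Day 8 value adjusted for the log Day 1 value, the stratification factors, baseline WHO Ordinal Scale score and number of co-existing conditions. Report a geometric mean ratio with 95% CI. For CRP, do the same at Day 4.
2. A shift table for each marker by arm, Day 1 status (at or below ULN, above ULN) against Day 8 status.

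Write the covariates and population out in full instead of cross-referring to 7.5.11. That section points to 7.5.6, which adjusts for baseline SOFA and excludes participants not admitted to ICU; neither belongs here. Section 7.5.5 ends with the same ICU exclusion, so 7.5.10 should also say that it does not apply to the incidence comparison.

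Cost: SAP wording, a small amount of programming, and a prespecified rule for values below the assay limit. Only participants with both samples contribute to the added model, so the number of pairs should be reported. No new data collection is needed. Because Part 2 carries the same endpoint, its analysis plan could take the same text.

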7.5.11 Viral Dynamics

Observed mean and mean change in log-transformed viral load from baseline on Days 1, 4, 8, 15, and 28 will be tabulated by treatment group and compared similar to the analysis of the SOFA score in Section 7.5.6.

Time-to-viral load undetectable (*i.e.*, <LOD) by nasopharyngeal swab is defined as the number of days from randomization to achieving undetectable viral load. That is:

(Date/Time to Undetectable Nasopharyngeal Swap – Date/Time of Randomization)/24.

Participants who are lost to follow-up or ended study early prior to achieve Undetectable Nasopharyngeal Swap will be censored at the day of the last obtained assessment. Median

number of days to undetectable will be tabulated by treatment group and compared in a way similar to the analysis of duration of COVID-19 symptoms in Section 7.5.3.

7.6 Safety Endpoints

Safety data will be summarized descriptively. No inferential statistics will be provided. All safety analyses and summaries will be based on the Safety analysis set.

7.6.1 Adverse Events

Treatment-emergent adverse events reported during the study will be coded using a MedDRA dictionary. Incidence of treatment-emergent adverse events will be summarized by treatment group and the following:

- Preferred term
- System organ class and preferred term.

These summaries will be presented for the following subsets:

- All adverse events
- Serious adverse events
- Drug-related adverse events
- All adverse events with severity \geq Grade 3
- All adverse events leading to death
- All adverse events leading to study treatment discontinuation.

A participant with multiple occurrences of the same adverse event or a continuing adverse event will only be counted once for tables reporting adverse events by preferred term and system organ class.

For tables reporting adverse events by severity, if a participant has multiple occurrences of an adverse event with the same organ class and preferred term, the most severe event will be presented. Adverse events with missing severity will be imputed to Grade 3. Additionally, for tables reporting adverse events by relationship, if a participant has multiple occurrences of an adverse event with the same organ class and preferred term, only the strongest relationship level will be presented in the relationship summary. Adverse events with missing relationship will be imputed as drug-related. Details on the treatment of missing data are provided in Section 11.2.

